8 TREATMENT PLAN

8.1 Agent Administration

See [Section 11](#) for further information

8.2 Radiation Therapy

Radiation will be administered in 3 fractions of 10 Gy, given every other day. As many as 3 lesions, each no greater than 5 cm in diameter on study tumor assessment scan, will be targeted. If more than 3 lesions meeting study criteria are present, those to be targeted will be selected based on the Radiation Oncologist and treating investigator’s shared judgment of those least likely to cause toxicity. The SBRT treatment planning, normal tissue constraints, and delivery methods used in this study have been previously described⁵¹.

8.3 General Concomitant Medication and Supportive Care Guidelines

Permitted Therapy

Premedication with antihistamines may be administered for any atezolizumab infusions after Cycle 1.

The following therapies should continue while patients are in the study:

- Oral contraceptives
- Hormone-replacement therapy
- Prophylactic or therapeutic anticoagulation therapy (such as low molecular weight heparin or warfarin at a stable dose level)

**Columbia University Irving Medical Center
Herbert Irving Comprehensive Cancer Center
CUMC IRB – AAAT0174**

- Palliative radiotherapy (e.g., treatment of known bony metastases) only if deemed appropriate by principal investigator
 - At minimum, palliative radiotherapy should not interfere with the assessment of tumor target lesions (e.g., the lesion being irradiated is not the only site of disease, as that would render the patient not evaluable for response by tumor assessments according to RECIST v1.1)
- Inactive influenza vaccinations
- Megestrol administered as an appetite stimulant
- Inhaled corticosteroids for chronic obstructive pulmonary disease
- Mineralocorticoids (e.g., fludrocortisone)
- Low-dose corticosteroids for patients with orthostatic hypotension or adrenocortical insufficiency

In general, investigators should manage a patient's care with supportive therapies as clinically indicated per local standards. Patients who experience infusion-associated symptoms may be treated symptomatically with acetaminophen, ibuprofen, diphenhydramine, and/or famotidine or another H2 receptor antagonist per standard practice (for sites outside the United States, equivalent medications may be substituted per local practice). Serious infusion-associated events manifested by dyspnea, hypotension, wheezing, bronchospasm, tachycardia, reduced oxygen saturation, or respiratory distress should be managed with supportive therapies as clinically indicated (e.g., supplemental oxygen and β 2-adrenergic agonists; see [Appendix 21.2.21.3](#)). All medications must be recorded on the appropriate Concomitant Medications eCRF.

Cautionary Therapy

Systemic corticosteroids and TNF- α inhibitors may attenuate potential beneficial immunologic effects of treatment with atezolizumab. Therefore, in situations where systemic corticosteroids or TNF- α inhibitors would be routinely administered, alternatives, including antihistamines, should be considered first by the treating physician. If the alternatives are not clinically appropriate, systemic corticosteroids and TNF- α inhibitors may be administered at the discretion of the treating physician except in the case of patients for whom CT scans with contrast are contraindicated (i.e., patients with contrast allergy or impaired renal clearance)

Systemic corticosteroids are recommended, with caution, at the discretion of the treating physician, for the treatment of specific adverse events when associated with atezolizumab therapy.

Refer to the atezolizumab **Investigator's Brochure** for additional information on the management of immune-mediated adverse events.

Prohibited Therapy

Any concomitant therapy intended for the treatment of cancer, whether health authority-approved or experimental, is prohibited for various time periods prior to starting study treatment, depending on the anti-cancer agent, and during study treatment until disease progression is documented and patient has discontinued study treatment. This includes, but is not

limited to, chemotherapy, hormonal therapy, immunotherapy, radiotherapy, investigational agents, or herbal therapy (unless otherwise noted).

The following medications are prohibited while on study, unless otherwise noted:

- Traditional herbal medicines, because their use may result in unanticipated drug-drug interactions that may cause or confound assessment of toxicity
- Denosumab; patients who are receiving denosumab prior to enrollment must be willing and eligible to receive a bisphosphonate instead while in the study
- Any live, attenuated vaccine (e.g., FluMist®) within 28 days prior to randomization, during treatment, or within 90 days following the last dose of atezolizumab/placebo
- Use of steroids to premedicate patients for whom CT scans with contrast are contraindicated (i.e., patients with contrast allergy or impaired renal clearance); in such patients, non-contrast CT scans of the chest and non-contrast CT scans or MRIs of the abdomen and pelvis should be performed

8.4 Duration of Therapy

In the absence of treatment delays due to adverse events, treatment may continue for 2 years (34 cycles) or until one of the following criteria applies:

- Disease progression
- Intercurrent illness that prevents further administration of treatment
- Unacceptable adverse events(s)
- Patient decides to withdraw from the study
- General or specific changes in the patient's condition render the patient unacceptable for further treatment in the judgment of the investigator

8.5 Duration of Follow Up

Patients will be followed for 2 years after completion or removal from study or until death, whichever occurs first. Patients removed from study for unacceptable adverse events will be followed until resolution or stabilization of the adverse event.

8.6 Criteria for Removal from Study

Patients will be removed from study when any of the criteria listed in [Section 6.5](#) applies. The reason for study removal and the date the patient was removed will be documented in the Case Report Form.

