Patients who discontinue treatment for reasons other than radiographic disease progression (e.g., toxicity) will continue scheduled tumor assessments at the same frequency as would have been followed if the patient had remained on study treatment (i.e., every 6 weeks [\pm 7 days] for the first 12 months following Cycle 1, Day 1 and then every 9 weeks [\pm 7 days] thereafter, regardless of treatment dose delays) until radiographic disease progression per RECIST v1.1, withdrawal of consent, study termination by the principal investigator, or death, whichever occurs first, regardless of whether patients start a new anti-cancer therapy.

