6.5 Early Withdrawal of Subjects

6.5.1 When and How to Withdraw Subjects

Patients have the right to voluntarily withdraw from the study at any time for any reason. In addition, the investigator has the right to withdraw a patient from the study at any time. Reasons for withdrawal from the study may include, but are not limited to, the following:

- Intolerable toxicity related to study treatment, including development of an immune-mediated adverse event determined by the investigator to be unacceptable given the individual patient's potential response to therapy and severity of the event
- Any medical condition that may jeopardize the patient's safety if he or she continues study treatment
- Investigator determines it is in the best interest of the patient
- Use of another non-protocol anticancer therapy
- Pregnancy
- Loss of clinical benefit as determined by the investigator after an integrated assessment of radiographic and biochemical data, local biopsy results (if available), and clinical status (e.g., symptomatic deterioration such as pain secondary to disease) (see Section

**Columbia University Irving Medical Center
Herbert Irving Comprehensive Cancer Center
CUMC IRB – AAAT0174**

6.5.2 for details)

- If one component of study treatment is discontinued permanently because of tolerability concerns, the patient may continue with other components of study treatment until disease progression if agreed upon by the investigator and patient
- If the patient fails to comply with the defined treatment plan and follow-up evaluations
- If the patient withdraws consent for continued participation

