6.5.3 Data Collection and Follow-up for Withdrawn Subjects

Every effort should be made to obtain information on patients who withdraw from the study. The primary reason for withdrawal from the study should be documented in the patient's medical records. If a patient requests to be withdrawn from the study, this request must be documented in the source documents and signed by the investigator. Patients who withdraw from the study before on-treatment study effects can be assessed will be replaced. If >3 patients (~20% of projected enrollment) require replacement, enrollment will be paused for the study team to review safety data until that point to assure safe continuation of the study. If it is determined that DLTs of special interest from liver-directed SBRT are occurring at a higher rate than would be expected in previous studies of chemoimmunotherapy and liver-directed SBRT, respectively, we will implement a dose reduction of SBRT as described in Section 9.6 for an additional 3 patients and reassess the rate of toxicity before completing enrollment.

If a patient withdraws from the study, the study staff may use a public information source (e.g., county records) to obtain information about survival status.

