5. Survival visits are to occur every 4 to 6 months from the date of the 6 month Follow-up visit. Survival follow-up information will be collected via telephone calls, patient medical records, and/or clinic visits. Study staff may use a public information source (e.g., county records), when permissible, to obtain information about survival status only.
6. For atezolizumab, the initial dose will be delivered over 60 (± 15) minutes. If the first infusion is well tolerated, all subsequent infusions may be delivered over 30 (± 10) minutes until loss of clinical benefit.
7. For carboplatin and etoposide, drug should be administered as described in [Section 11](#)
8. Liver directed radiation with three doses of 10Gy delivered on alternate days up to three liver lesions measuring no greater than 5 cm each should be started within 7 (+/-3) days of C2D1
9. CT scans (with oral/IV contrast unless contraindicated) or MRI scans of the chest and abdomen.
10. A CT scan of the pelvis is required at screening and as clinically indicated or as per local standard-of-care at subsequent response evaluations.
11. Perform every 6 weeks (± 7 days) (approximately every two cycles) for 12 months following Cycle 1, Day 1 and then every 9 weeks (± 7 days) thereafter, regardless of treatment delays, until radiographic disease progression, withdrawal of consent, death, or study termination by the Sponsor, whichever occurs first. Patients who continue treatment beyond radiographic disease progression per RECIST v1.1 will continue to undergo tumor assessments every 6 weeks (± 7 days) or sooner if symptomatic deterioration occurs. For these patients, tumor assessments should continue every 6 weeks (± 7 days), regardless of time on study, until study treatment is discontinued.
12. If the patient discontinued study treatment for any reason other than disease progression (e.g., toxicity), tumor assessments will continue at the same frequency as would have been followed if the patient had remained on study treatment until radiographic disease progression, withdrawal of consent, death, or study termination by the principal investigator, whichever occurs first, even if the patient starts another anti-cancer therapy after study treatment discontinuation, unless consent is withdrawn.
13. Laboratory assessments to be done within 2 days prior to study drug infusion.

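### Sections 6.5.1 and 8.6 remove patients from the study for events after which Section 5.2 and the calendar require scans to continue, so sites may differ on whether six-month PFS is observed

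*Combined protocol and SAP*

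**What the plan says.** Two sets of passages in the combined protocol and SAP govern the patient who stops treatment before progression.

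**Removal.** Section 6.5.1 opens with "Reasons for withdrawal from the study may include, but are not limited to, the following". Its list includes "Intolerable toxicity related to study treatment, including development of an immune-mediated adverse event" and "Use of another non-protocol anticancer therapy", together with loss of clinical benefit and non-compliance. Section 8.6 turns the list into a rule: "Patients will be removed from study when any of the criteria listed in" Section 6.5. For patients who have left, Section 6.5.3 says "Every effort should be made to obtain information on patients who withdraw from the study" and allows a public-source check of survival status. It names no scans.

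**Continued scanning.** Section 5.2 says "Patients who discontinue treatment for reasons other than radiographic disease progression (e.g., toxicity) will continue scheduled tumor assessments at the same frequency", and that this holds "regardless of whether patients start a new anti-cancer therapy". Calendar note 12 (Section 12) agrees: "even if the patient starts another anti-cancer therapy after study treatment discontinuation, unless consent is withdrawn". The calendar also marks CT in the survival follow-up column and ties the mark to note 12. The events that end scanning are RECIST progression, consent withdrawal, termination of the study and death. Removal under Section 6.5 is not among them.

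Section 8.5 follows patients for two years after removal without mentioning scans. Section 15.2 restricts the primary analysis to treated, eligible patients with a six-month outcome that can be evaluated. It also replaces those who withdraw before on-treatment effects can be assessed.

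**The concern.** For toxicity and for new anticancer therapy, one set of sections ends participation in the study and the other requires tumor assessments to go on. A site working from Sections 8.6 and 6.5.3 could reasonably stop scanning. A site working from Section 5.2 and the calendar would continue. With three centers projected, that choice should not be local.

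The primary endpoint is exposed because of Section 15.2. A patient removed without progression, alive and not scanned again, may have no six-month outcome that can be evaluated and so leave the PFS6 denominator. The loss would probably be informative, since removal follows toxicity, loss of benefit or a change of therapy. The go rule is at least 6 of 16, so each patient is 1/16 = 6.25 percentage points and a single patient can decide the result.

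**Working it through.** **1. One patient under both readings.** Suppose a patient stops for toxicity at week 10 without progression and starts another therapy at week 14.

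| Source | Consequence |
|---|---|
| Section 5.2, calendar note 12 | Scans continue every 6 weeks, so at weeks 12, 18 and 24 (each ± 7 days) |
| Sections 6.5.1 and 8.6 | Removed from study, at the latest when the new therapy starts |
| Section 6.5.3 | Best-effort information and a survival look-up; no scan required |
| Section 8.5 | Two years of follow-up; scans not mentioned |
| Section 15.2 | In the primary analysis only if the six-month outcome can be evaluated |

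On the first reading PFS6 is observed. On the second it may not be.

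**2. The plan's design (Section 15.1).** Inputs: n = 16, go if X ≥ 6, null rate 0.20, alternative 0.45, one-sided exact binomial test, type I error limit 0.10, power 0.80, dropout 10%.

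- Type I error: P(X ≥ 6 | n = 16, p = 0.20) = 0.0817
- Power: P(X ≥ 6 | n = 16, p = 0.45) = 0.8024
- Accrual: 16/(1 − 0.10) = 17.8, rounded up to 18

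The stated design reproduces.

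**3. If removed patients would all have failed.** The documents give no removal rate, so the fraction f of treated patients removed is an assumption. Suppose they are excluded and accrual continues until 16 patients are evaluable. A true rate of 0.20 then appears as 0.20/(1 − f).

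| f | Apparent rate | P(X ≥ 6 of 16) | Treated to reach 16: 16/(1 − f) |
|---|---|---|---|
| 0 | 0.200 | 0.082 | 16.0 |
| 5% | 0.211 | 0.100 | 16.8 |
| 10% | 0.222 | 0.123 | 17.8 |
| 15% | 0.235 | 0.153 | 18.8 |

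The 0.10 limit is reached at about 5%. The 5% and 10% rows fit within the 18 accrued. The 15% row needs about 19, so it relies on replacement.

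**4. If removed patients would all have been progression free.** A true rate of 0.45 appears as (0.45 − f)/(1 − f). Power falls to 0.731, 0.637 and 0.520 for f = 5%, 10% and 15%. The bias then runs the other way.

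**5. If outcomes are lost and not replaced.** Keep the cut-off at 6, with a true rate of 0.45:

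| Outcomes lost of 16 | n | Power |
|---|---|---|
| 0 | 16 | 0.802 |
| 1 | 15 | 0.739 |
| 2 | 14 | 0.663 |
| 3 | 13 | 0.573 |

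These are losses beyond the allowance of 18 − 16 = 2 patients.

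**The case against.** The strongest reply is that the protocol already settles the matter. Section 5.2 and note 12 are the specific rules on scanning, and they list what ends it. The calendar marks CT in survival follow-up. Section 8.5 keeps removed patients in follow-up, so removal does not end contact. Section 8.4 lists reasons to end therapy separately from Section 8.6, so the protocol does in places separate stopping treatment from leaving the study. Section 6.5.1 is itself permissive. All of this is correct. A reader might infer that PFS6 data are lost by rule; the documents do not support that, because no section says scans stop on removal.

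A reader might also infer that the lost patients are failures the trial ought to count. Stopping for toxicity is not a PFS6 event: Section 13.7 counts progression or death, and toxicity is assessed separately from first treatment. Deaths before six months can still be found through the survival look-up.

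Nor can it be said that removals will use up the dropout allowance. No removal rate is given, and the 10% may already cover such losses.

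Finally, the Section 6.5.1 item on stopping one component permits the patient to continue the others. It is not a reason to leave, and it shows that Section 8.6 cannot apply literally to every item.

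What survives is that Section 8.6 is mandatory, Section 6.5.3 names no scans, and nothing says which text prevails.

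**Conclusion.** This is an internal inconsistency that should be corrected. It is not a flaw in the sample size, which reproduces. Whether any PFS6 outcome is lost depends on how each site reads the text, and on Section 15.2 leaving such patients out of the primary analysis.

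The direction of bias is not determined. The figures are illustrations at assumed rates and in extreme cases, in which every removed patient would have failed or every one would have been progression free. With 5% to 15% removed, all of them failures and replaced, the false-go probability rises from 0.082 to between 0.100 and 0.153. Losing 1 to 3 of 16 outcomes without replacement lowers power from 0.802 to between 0.739 and 0.573. Mixed outcomes among removed patients would give smaller shifts than the one-sided cases.

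**What to change.** Reconcile Sections 5.2, 6.5.1, 6.5.3, 8.5, 8.6 and the calendar by distinguishing the end of study treatment from withdrawal from study follow-up. State in Sections 6.5.3 and 8.6 that a patient taken off treatment under Section 6.5 without RECIST progression stays on the Section 5.2 and note 12 scan schedule, and in survival follow-up, until RECIST progression, consent withdrawal, termination of the study or death. Have Section 8.5 name those scans.

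Keep the Section 6.5.1 item on continuing other components as a permission, outside the removal criteria. No change is proposed to when treatment is stopped. Correct the cross-reference in Section 11.2, which points to Section 5.5 for the withdrawal criteria; Section 5 ends at 5.3.

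The cost is an amendment to the wording. Section 5.2 and note 12 already require the scans.

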9 DOSING DELAYS/DOSE MODIFICATIONS

9.1 General Notes Regarding Dose Modification

Reasons for dose modifications or delays, the supportive measures taken, and the outcomes will be documented in the patient's chart and recorded on the eCRF. The severity of adverse events will be graded according to the NCI CTCAE v5.0 grading system.

- For any concomitant conditions already apparent at baseline, the dose modifications will apply according to the corresponding shift in toxicity grade, if the investigator feels it is appropriate. For example, if a patient has Grade 1 asthenia at baseline that increases to Grade 2 during treatment, this will be considered a shift of one grade and treated as Grade 1 toxicity for dose-modification purposes.
- When several toxicities with different grades of severity occur at the same time, dose modifications should be made according to the highest grade observed.
- If, in the opinion of the investigator, a toxicity is considered to be due solely to one component of the study treatment (i.e., atezolizumab, carboplatin, etoposide, or radiation) and the dose of that component is delayed or modified in accordance with the guidelines below, other components may be administered if there is no contraindication.
- When treatment is temporarily interrupted because of toxicity caused by atezolizumab, carboplatin, etoposide, or radiation, the treatment cycles should be restarted such that the atezolizumab infusions remain synchronized and aligned with the chemotherapy schedule.
- If, in the opinion of the investigator, a toxicity is considered to be due solely to one chemotherapy drug, the dose of the other chemotherapy drug does not require modification. The investigator may use discretion in modifying or accelerating the dose modification guidelines described below depending on the severity of toxicity and an assessment of the risk versus benefit for the patient, with the goal of maximizing patient compliance and access to supportive care.

9.2 Atezolizumab Dose Modification

There will be no dose reduction for atezolizumab in this study. Patients may temporarily suspend study treatment for up to 105 days beyond the last dose if they experience an adverse event that requires a dose to be held. If atezolizumab is withheld because of adverse events for more than 105 days beyond the last dose, then the patient will be discontinued from atezolizumab treatment. If a patient must be tapered off steroids used to treat adverse events, atezolizumab may be withheld for additional time beyond 105 days from the last dose until steroids are discontinued or reduced to prednisone dose (or dose equivalent) ≤ 10 mg/day. The acceptable length of interruption will depend on agreement between the investigator and the Medical Monitor. Dose interruptions for reason(s) other than adverse events, such as surgical procedures, may be allowed with Medical Monitor approval. The acceptable length of interruption will depend on agreement between the investigator and the Medical Monitor.

Toxicities associated or possibly associated with atezolizumab treatment should be managed according to standard medical practice. Although most immune-mediated adverse events observed with immunomodulatory agents have been mild and self-limiting, such events should

be recognized early and treated promptly to avoid potential major complications. Discontinuation of atezolizumab may not have an immediate therapeutic effect and, in severe cases, immune-mediated toxicities may require acute management with topical corticosteroids, systemic corticosteroids or other immunosuppressive agents. The investigator should consider the benefit-risk balance a given patient may be experiencing prior to further administration of atezolizumab. Atezolizumab should be permanently discontinued in patients with life-threatening immune-mediated adverse events.

The primary approach to Grade 1–2 immune-related adverse events (irAEs) is supportive and symptomatic care with continued treatment with atezolizumab; for higher grade irAEs, atezolizumab should be held and oral/parenteral steroids administered. Recurrent Grade 2 irAEs may also mandate holding atezolizumab or the use of steroids. Consideration for benefit/risk balance should be made by the investigator, with consideration of the totality of information as it pertains to the nature of the toxicity and the degree of clinical benefit a given patient may be experiencing prior to further administration of atezolizumab. Atezolizumab should be permanently discontinued in patients with life-threatening immune-related adverse events.

Refer to the atezolizumab **Investigator's Brochure** for more detailed information regarding dose modification.

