9.6 Potential Overlapping Toxicities

**Columbia University Irving Medical Center
Herbert Irving Comprehensive Cancer Center
CUMC IRB – AAAT0174**

The risk of overlapping toxicities between atezolizumab, carboplatin, and etoposide is thought to be minimal. Nevertheless, the attribution and management of certain adverse events that have been associated with each agent separately (e.g., hepatotoxicity, skin and gastrointestinal toxicity) may be ambiguous when the agents are administered together. It is theoretically possible that allergic or inflammatory AEs associated with carboplatin and etoposide (e.g., dermatitis, infusion-associated symptoms) could be exacerbated by the immunostimulatory activity of atezolizumab.

Toxicities should initially be managed according to the recommendations in [**Sections 9.1-9.3**](#) with dose holds and modifications (if applicable) applied to the component of the study drug judged to be the primary cause. For severe (Grade 3) or persistent Grade 1–2 diarrhea, an endoscopic evaluation should be considered. Additional tests, such as autoimmune serology or biopsies, may be used to determine a possible immunogenic etiology for adverse events listed above. If, in the opinion of the investigator, atezolizumab is a potential inciting factor, the dose of atezolizumab may be held for a maximum of 105 days beyond when the next dose should have been given (see [**Section 9.1**](#)). Prompt symptomatic management is appropriate for mild immune-mediated adverse events. In severe cases, immune-mediated toxicities may be acutely managed with systemic corticosteroids or TNF- α inhibitors. These cases should be discussed with the Medical Monitor.

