11.4 Preparation and Administration of Study Drug

Atezolizumab, carboplatin and etoposide are prepared according to the recommendations from the manufacturers' label. All drugs are obtained through standard commercial pharmacies.

Any overdose or incorrect administration of any of the study treatments should be noted in the patient's medical records and reported according to [**Section 10.4**](#) (Special Situations Reports). Adverse events associated with an overdose or incorrect administration of any of the study treatments should be recorded in the patient's medical records

Guidelines for dosage modification treatment interruption or discontinuation for patients who experience adverse events are provided in [**Section 9**](#).

Atezolizumab Administration

Administration of atezolizumab will be performed in a monitored setting where there is immediate access to trained personnel and adequate equipment and medicine to manage potentially serious reactions. For anaphylaxis precautions, see [**Appendix 21.2**](#). Atezolizumab infusions will be administered per the instructions outlined in **Table 5**.

Table 5 Administration of First and Subsequent Atezolizumab Infusions

First Infusion	Subsequent Infusions

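### At a first Grade 2 immune-related event, Section 9.2 continues atezolizumab where the attached tables hold it (pulmonary, hepatic over 5 days, colitis, ocular, neuropathy), and no text says which rule governs

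*Combined protocol and SAP*

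**What the plan says.** Section 9.2 gives a general rule by grade. For Grade 1–2 immune-related events the primary approach "is supportive and symptomatic care with continued treatment with atezolizumab; for higher grade irAEs, atezolizumab should be held" and oral or parenteral steroids given. It then adds: "Recurrent Grade 2 irAEs may also mandate holding atezolizumab or the use of steroids". On stopping for good it says: "Atezolizumab should be permanently discontinued in patients with life-threatening immune-related adverse events". Investigator benefit/risk judgment applies throughout.

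The attachment to the protocol contains management tables by organ. Its pulmonary table withholds atezolizumab for up to 12 weeks at Grade 2 and starts corticosteroids equivalent to 1–2 mg/kg/day prednisone. Its hepatic table does the same for Grade 2 events lasting more than 5 days. Its colitis, ocular and neuropathy rows also withhold at Grade 2.

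The cross-references do not connect the two:

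- Section 9.2 sends the reader to the Investigator's Brochure "for more detailed information regarding dose modification".
- Section 8.3 does the same "for additional information on the management of immune-mediated adverse events".
- Section 9.6, having named hepatotoxicity, skin and gastrointestinal toxicity as hard to attribute, says: "Toxicities should initially be managed according to the recommendations in" Sections 9.1–9.3.
- Section 11.4 says: "Guidelines for dosage modification treatment interruption or discontinuation for patients who experience adverse events are provided in" Section 9.

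**The concern.** Two parts of one protocol give different instructions for the same event. An investigator who applies Section 9.2's stated default may continue dosing with supportive care through a first Grade 2 pneumonitis, or through a Grade 2 hepatic event that has lasted more than 5 days. One who opens the attachment withholds the drug and starts systemic steroids. Both can claim to follow the protocol.

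The hepatic case matters most here, because the trial adds liver SBRT to a drug associated with immune-related hepatitis. Section 9.5 itself lists hepatopancreaticobiliary toxicity and excess immune-related events as matters to watch. With three centers projected, and affiliate monitoring under Section 18.7 covering treatment compliance, monitors also lack a single rule to check against.

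**Working it through.** There is no design figure to reproduce. The check sets the two texts side by side and then works out what the difference means for dosing.

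**Step 1. The rules compared.**

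| Event | Section 9.2 | Attached table | Does the attachment direct use of its table? |
|---|---|---|---|
| First Grade 2 pulmonary | Continue, supportive care | Hold up to 12 weeks; prednisone equivalent 1–2 mg/kg/day | No; says only where guidelines are found |
| Grade 2 hepatic, over 5 days | Continue, supportive care | Hold up to 12 weeks; prednisone equivalent 1–2 mg/kg/day | No |
| First Grade 2 diarrhea or colitis | Continue, supportive care | Hold up to 12 weeks; systemic steroids if recurrent or over 5 days | No |
| First Grade 2 ocular | Continue, supportive care | Hold up to 12 weeks; topical steroid and immunosuppressive treatment | No |
| First Grade 2 neuropathy | Continue, supportive care | Hold up to 12 weeks; treat per institution | No |
| Grade 2 myocarditis | Continue, supportive care | Hold up to 12 weeks; consider steroids | Yes |
| Grade 2 renal | Continue, supportive care | Hold up to 12 weeks; prednisone equivalent 1–2 mg/kg/day | Yes |
| Grade 3 pulmonary or hepatic | Hold and give steroids | Permanent stop and steroids; re-challenge possible after full recovery | No |

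A first Grade 2 event falls under Section 9.2's continue rule, because that section raises a hold at Grade 2 only for recurrence, and then only as a possibility.

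**Step 2. Is there a tie-break?** For the first five rows, none was found. All four pointers listed above lead to the Brochure or back to Section 9, and none names the tables. For myocarditis and renal events the attachment does say to treat according to its own table, but Section 9.2 does not acknowledge this.

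**Step 3. Size per event.**

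- Section 9.2 default at a first Grade 2 event: 0 doses held.
- Table limit: 12 weeks × 7 = 84 days; 84 / 21 = 4 scheduled doses. Footnote a allows longer while steroids are tapered.
- Minimum once systemic steroids are started (the pulmonary and hepatic rows): footnote b requires a taper over at least 1 month before resuming. Taking a month as at least 28 days, 28 > 21, so at least 1 scheduled dose is missed or delayed.

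These are limits taken from the text, not expected patient numbers. No rate in the documents isolates Grade 2 pulmonary events or Grade 2 hepatic events over 5 days. The hepatitis figure of 6.1% in Section 4.1.4 pools Grades 1 and 2 and gives no duration.

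**The case against.** The best defense is that Section 9.2 states a general principle and the tables supply the detail. It speaks of a primary approach, calls for standard medical practice, prompt recognition and benefit/risk judgment before further dosing, and refers to the Brochure. Section 9.6 adds that, if atezolizumab is a potential cause, "the dose of atezolizumab may be held for a maximum of 105 days beyond when the next dose should have been given", with no grade attached. Many rows also agree with Section 9.2: Grade 2 dermatologic events, Grade 2 hepatic events of up to 5 days, and Grade 3 holds for colitis, dermatologic events and myositis.

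This shows that an investigator may hold the drug. It does not show that the protocol tells them to, and no text states the general-versus-specific reading. The Brochure is not among the documents, so whether it would settle the matter is unknown.

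Three stronger readings are tempting and do not stand:

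- **That Section 9.2 allows a permanent stop only for life-threatening events.** It does not say so. It also stops atezolizumab after a hold of more than 105 days from the last dose, with an exception for steroid taper, and Section 6.5.1 allows withdrawal for an immune-mediated event the investigator finds unacceptable. Stricter rows for Grade 3, or for any grade, can therefore coexist with it.
- **That every organ table lacks a governing instruction.** The myocarditis, meningoencephalitis, renal, myositis and HLH/MAS sections direct use of their own tables.
- **That Grade 3 is as sharp a conflict as Grade 2.** Both texts stop dosing. They differ on whether the stop is permanent, and most table rows allow re-challenge.

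**Conclusion.** The concern holds for first Grade 2 pulmonary, colitis, ocular and neuropathy events and for Grade 2 hepatic events over 5 days. There the protocol contains two incompatible defaults and no ranking. The pulmonary and hepatic cases are the clearest, since they differ on both the hold and systemic steroids. Per event the difference runs from no planned interruption to a hold of up to 84 days, extendable for the steroid taper. For myocarditis and renal events the defect is narrower: the attachment settles the question and Section 9.2 fails to say so.

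The plan is wrong as written on this point, as an internal safety inconsistency, and it should be corrected. The conclusion rests on the text alone. It assumes nothing about the Brochure and claims no number of affected patients. A reader might infer that the inconsistency biases the primary result; the documents give no basis for that, and the sample size, the exact binomial test and the 6-month PFS definition are unaffected.

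**What to change.** By amendment, add to Section 9.2:

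1. The attached management tables govern withholding, steroids and discontinuation for any event they cover.
2. The general approach by grade in Section 9.2 applies only to immune-related events that no table covers.
3. The permanent stop for life-threatening immune-related events continues to apply unless a table row expressly says otherwise. Rows that name Grade 4 and only withhold (symptomatic adrenal insufficiency, hyperglycemia, amylase/lipase elevation) would then follow the table.

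Cite the tables in Sections 9.6 and 11.4. Cite them by title, because the attachment reuses table numbers that also appear in the body (Table 1 is carboplatin dosing in Section 9.3.1 and pulmonary events in the attachment). Point Section 11.4's infusion-reaction reference to the attached infusion-reaction and cytokine-release table: it now names Appendix 21.3, whose text is the VALG staging scheme. Check the tables against the current Brochure before giving them precedence.

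The cost is three sentences and a few cross-reference edits, with no change to sample size, data collection or analysis.
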